- End stage renal disease as defined by patients requiring hemodialysis at least twice weekly
- Polytrauma, defined as:
 - Concurrent upper or lower extremity fracture, pelvis fracture, spine fracture, rib fractures, or facial fractures
 - Blunt chest or abdominal trauma resulting in diagnosed organ injury
 - Head trauma resulting in intracranial bleed or diagnosed concussion
- Allergy to amide-type local anesthetics
- Prisoners (unlikely to be accessible for follow-up)

6. Study-Wide Number of Subjects

This is a multi-center study being conducted in conjunction with the University of Kentucky. The total recruitment goal is 60 patients, with a goal enrollment of 30 patients at University of Massachusetts, and 30 patients at University of Kentucky.

Recent studies evaluating regional nerve blocks in hip fractures have shown an average morphine sulfate equivalent of 3.5 +/- 0.52 mg/d in the first 3 postoperative days²⁶. That same study showed a 33% reduction in morphine equivalents (3.5 mg/d vs 2.1 mg/d). Assuming a similar effect size, this study would require only 8 patients group to be powered to 80% with a significance level of 0.05. With a target recruitment goal of 50 patients, the study would be powered to detect differences as low as 0.42 mg/d (a 12% effect size). Assuming a 10-20% loss to follow-up, we aim to recruit a total of 60 patients studywide (i.e. 30 at each site).

7. Study-Wide Recruitment Methods

Recruitment methods will be the same at both University of Massachusetts and University of Kentucky. Refer to [24. Recruitment Methods](#) for details of recruitment methods at University of Massachusetts.

8. Study Timelines

- Duration of an individual subject's participation in the study

An individual subject's participation in the study begins at enrollment and ends after the 30 day post-op follow-up period.

- Duration anticipated to enroll all subjects

From recent internal data review, we treat between 250-300 hip fractures annually at UMMMC. We anticipate 10-25% of patients will be both eligible and willing to enroll in the study, so to enroll 30 patients should take 6-12 months.

- Estimated date for the investigators to complete this study (complete primary analyses)

Primary analysis should be completed once the final cohort of patients complete their 30 day study window, so we expect 13-14 months after initiation of enrollment.

9. Study Endpoints

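### Three planning figures do not agree: a 33% reduction beside means that give 40%, a required number of 8 not labelled per group or total, and a local goal of 25 against 30

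*Protocol*

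**What the plan says.** **Effect size.** Section 6 of the protocol and the power analysis in the SAP take from a nerve-block study "an average morphine sulfate equivalent of 3.5 +/- 0.52 mg/d" over the first three postoperative days. They continue: "That same study showed a 33% reduction in morphine equivalents (3.5 mg/d vs 2.1 mg/d". Section 16 repeats the 33% without the means.

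**Required number.** Both documents conclude that "this study would require only 8 patients group to be powered to 80% with a significance level of 0.05". Neither says what the 0.52 is, gives a spread for the treated arm, or states sidedness or allocation ratio. The SAP names Student's t-test for continuous variables.

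**Detectable difference.** Both documents add: "With a target recruitment goal of 50 patients", "the study would be powered to detect differences as low as 0.42 mg/d (a 12% effect size".

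**Enrolment.** Section 6 sets 60 in total, "with a goal enrollment of 30 patients at University of Massachusetts, and 30 patients at University of Kentucky". After allowing for 10-20% loss it repeats: "we aim to recruit a total of 60 patients studywide (i.e. 30 at each site". Section 8 plans local accrual on the same basis: "so to enroll 30 patients should take 6-12 months". Section 25 gives the University of Massachusetts goal as 25 and refers the reader to section 6. Section 18 says only that the two sites' goals are equivalent.

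**The concern.** A reader uses these figures to check the design, and a site uses them to know its target.

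- The percentage and the two means beside it describe different effects, so it is unclear which effect the required number was computed for.
- The required number lacks the word that would say whether it is per group or in total. If it is per group, it looks too large for the spread quoted just before it.
- One site has two enrolment targets.

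If the errors reached the design, the trial could be wrongly sized, or one site could stop five patients short.

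**Working it through.** **Inputs.** From section 6 and the SAP: means 3.5 and 2.1 mg/d, spread 0.52, power 80%, significance level 0.05, 50 patients. From the SAP: Student's t-test. Assumed, because not stated: 0.52 is the SD in both arms, the test is two-sided, and allocation is 1:1.

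**1. Reproduce the plan's 0.42 mg/d.** With 25 per group and SD 0.52, the exact (noncentral) t-test gives 0.4205 mg/d, and 0.42/3.5 = 12%. Both match the plan. The normal approximation, (1.960 + 0.842) × 0.52 × √(2/25), gives 0.412, and a one-sided t-test gives 0.371. The assumed inputs therefore fit best. Working backwards, 0.42 (0.415 to 0.425 before rounding) implies an SD of 0.519 (0.513 to 0.526).

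**2. Percentage.** (3.5 − 2.1)/3.5 = 40.0%. Rounding of the means allows only (3.45 − 2.15)/3.45 = 37.7% to (3.55 − 2.05)/3.55 = 42.3%. With 2.1 as the base it is 66.7%. A 33% reduction from 3.5 is 3.5 × 0.33 = 1.155 mg/d, a treated mean of about 2.35.

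**3. Required number at SD 0.52.** Power by exact t-test:

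| Per group | 1.4 mg/d | 1.155 mg/d |
|---|---|---|
| 3 | 69.7% | 54.1% |
| 4 | 88.4% | 74.5% |
| 5 | 96.0% | 86.6% |
| 8 | 99.9% | 98.5% |

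So 80% power needs 4 per group for 1.4 mg/d and 5 per group for 1.155 mg/d. The normal approximation, n per group = 2(1.960 + 0.842)² × 0.52²/Δ², gives 2.17, rounded up to 3, and 3.18, rounded up to 4. Eight in total therefore fits 1.4 mg/d by t-test (2 × 4), or 1.155 mg/d by normal approximation (2 × 4).

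**4. Can 8 per group and 0.42 share one SD?** Eight is the minimum per group only if 7 falls short of 80% power and 8 reaches it. That needs an SD of 0.858 to 0.929 for 1.4 mg/d, or 0.708 to 0.767 for 1.155 mg/d. At those SDs, 25 per group would detect 0.694 to 0.751 or 0.573 to 0.620 mg/d, not 0.42. The answer is no.

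**5. Enrolment.** 50/0.9 = 56 and 50/0.8 = 63, so 60 lies within the stated loss range, and 60/2 = 30 per site. The 25 equals 50/2, half the target before the loss allowance. That may be where it came from, but the documents do not say.

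Detectable difference at SD 0.52 if one or both sites stopped at 25:

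| Enrolled | 10% loss: left, mg/d | 20% loss: left, mg/d |
|---|---|---|
| 60 | 54, 0.404 | 48, 0.430 |
| 55 | 49, 0.425 | 44, 0.450 |
| 50 | 45, 0.444 | 40, 0.473 |

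With 40 left, power for 1.155 mg/d is above 99.9% at SD 0.52, 99.6% at SD 0.77 and 96.9% at SD 0.93. Applying the full loss rate to 72-hour inpatient outcomes is a worst case.

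**The case against.** The best defence is that the required number is badly worded but correctly calculated. One set of inputs (means 3.5 and 2.1, SD 0.52, two-sided t-test, 1:1) gives both 4 per group, hence 8 in total, and 0.42 mg/d for 50 patients. On that reading a recomputed number would again be 8. This stands as a plausible reading, and the documents do not exclude it. It does not clear the text: the word that remains in the sentence points towards a per-group figure, and by t-test 8 in total goes with a 40% reduction, not the printed 33%.

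It can also be said that section 16 quotes 33% without means and so does not contradict itself. That is correct; section 16 is affected only if the 33% proves wrong. Section 25 sends the reader to section 6, so a site is unlikely to stop at 25, and the scenarios above are hypothetical. Section 6 also largely explains how 50 becomes 60. These points limit the importance of the errors but do not remove the mismatches.

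**Conclusion.** The concern holds, as a minor one.

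- **33% against 40%:** a plain mismatch that needs no assumption and that rounding cannot explain. The two versions differ by 1.4 − 1.155 = 0.245 mg/d. The documents do not show whether the percentage or a mean is wrong.
- **The 8:** ambiguous as written. Read per group, it is 8 where 4 or 5 would do, and it cannot come from the same SD as 0.42. Read as a total, it is plausible. This part rests on 0.52 being a common SD, a two-sided test and 1:1 allocation; the reproduced 0.42 supports these inputs.
- **25 against 30:** a direct contradiction that needs no assumption.

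The 50 and the 60 depend on neither the 33% nor the 8. If both sites stopped at 25 and 20% were lost, the detectable difference at SD 0.52 would move from 0.430 to 0.473 mg/d.

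**What to change.** 1. Check the cited study and make the percentage and the two means agree in section 6 and the SAP. Correct section 16 too if the 33% changes.
2. In section 6 and the SAP, recompute the required number from the corrected effect and say whether it is per group or total. State what 0.52 is, the SD assumed in each arm, the sidedness and the allocation ratio.
3. Change the local goal in section 25 to 30, to match sections 6 and 8. If it is what is meant, say in section 6 that 50 is the number wanted after loss and 60 the number enrolled, since both are now described as recruitment goals.

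The cost is a text correction to the protocol and SAP. The design, the tests and the planned enrolment of 60 do not change.

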- **Hypothesis:** We hypothesize that total episodes of delirium will be decreased in the liposomal bupivacaine group.

3. **Determine if Exparel is cost-effective in hip fracture patients.** The costs associated with increased narcotic usage, prolonged stay, resources, and complications can be significant. The use of liposomal bupivacaine may lead to decreased resource utilization to care for hip fractures. We will conduct an economic analysis evaluating total inpatient hospitalization costs including costs associated with length of stay, medication requirements, and resources associated with consultations and diagnostic evaluations. These costs will be compared against the cost of Exparel administration to evaluate the net cost effect of the intervention.

- **Hypothesis:** We hypothesize that the net cost of inpatient care will be decreased when compared to standard of care.

4. Background

Osteoporotic fragility fractures of the hip are common in the geriatric population, are increasing in frequency, and represent a growing social and economic burden^{1,2}. Pain control after surgical treatment is an area of growing interest³, as improvement in post-injury pain is often an important indication for surgical treatment of hip fractures^{4,5}.

Typically a mainstay of post-operative pain control, the use of opiates has come under increasing scrutiny, as it has been shown to be associated with delirium, respiratory depression, and even may even lead to addiction or abuse in the medically frail geriatric population⁶. These concerns have led to efforts to minimize the use of post-operative opiates in hip fracture patients. In that context, a treatment that could reduce the necessity of post-op narcotics while still improving pain control would be potentially valuable.

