- **Primary Outcome Variables:** Total morphine equivalents in the post-operative period for 24, 48, and 72 hours, CAM score and average Pain Visual Analog Scale
- **Secondary Outcome Variables:** Length of stay, discharge disposition, timing and participation with inpatient physical therapy, complications and 30 day readmission.

10. Procedures Involved

- **Patient identification:** Patients will be identified on morning intake rounds by the trauma team and the research staff who are present daily to screen and enroll patients.
- **Screening/Enrollment:** The research staff will review the charts to identify patients meeting the inclusion/exclusion criteria. Patients will be approached for study participation and enrolled in the study prior to surgery. For potential participants, the research staff will interview the patients, confirm willingness to participate and inclusion/criteria.
 - We will utilize a Mini-COG (Screening for Cognitive Impairment in Older Adults)²⁷. A score of <4, which has been shown to have high sensitivity for dementia screening will define cognitive impairment and will preclude enrollment.
 - At time of enrollment, preoperative demographics will be recorded which will include age, sex, comorbidities, current use of anti-epileptic/anti-depressive medications for pain control, type of surgical approach, pre-ambulatory status and implant class.
 - After this review and screening, the patient will be given the opportunity to ask researchers questions about the study. It will be reiterated to all patients during preoperative discussions that their enrollment status in no way will affect their ability to get adequate post-operative pain control.
- **Randomization:** Randomization will be done through the research pharmacy. Participants will undergo block randomization (block size: 10) through a computer-generated algorithm.

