- **Treatment:** Surgical treatment will be performed according to the attending surgeon and is independent of the study. At the conclusion of surgery, they will receive a subcutaneous injection of either Exparel placebo. Patients will receive operative treatment of the hip fracture per the operating surgeon. At the conclusion of surgery, Exparel will be given in 20cc doses, diluted with 40cc of normal saline to make 60cc of total injection volume. The injection solution contains a total of 266mg free base bupivacaine (equivalent of 300 mg bupivacaine HCl). The research pharmacy will prepare the injection solution to contain either Exparel or placebo solution. In intra-capsular arthroplasty cases, the solution will be injected circumferentially into the capsule, surrounding musculature, and subcutaneous layer. In cases with extra-capsular fractures treated with sliding hip screws or cephalomedullary nails, the solution will be administered in the deep tissue and muscles around the fascial incisions as well as in the subcutaneous layer. At the time of medicine or placebo administration, the operating room circulating nurse will create a log entry for Exparel administration in the medication administration record (MAR). This is the section of the medical record where all medications must be recorded, and will be consulted prior to delivery of any other local anesthetic agents, which will serve to limit the additional exposures and minimize the risk of toxicity.
- **Post-operative inpatient care:** While admitted to the hospital, patients will receive medical care per routine, including a standardized post-operative pain control regimen. Post-operatively, all patients will receive a uniform pain control protocol consistent with the current standard of care. We have worked with our anesthesia team to create a consensus-driven protocol to ensure patients are

evaluated for pain and having pain treated in an appropriate and uniform manner. The written protocol is included at the conclusion of this document as Appendix A. We will collect the following data from inpatient hospitalization.

- As a part of the research study regiment, delirium will be assessed using the Confusion Assessment Method (CAM)²⁸, which will be administered 6 hours following surgery, post-operative day 1, 2 and 3 between 8AM-12PM, when a provider is called to the bedside to evaluate the patient for confusion, and also by nursing staff at each nursing shift (Q12).

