- Adverse events will be monitored and recorded during hospitalization following standard of care regiment and later be used and accessed for data collection of the research study. The adverse events monitored and recorded will include: alteration of mental status, respiratory depression, wound complications, fixation-related complications.
- The following information will be accessed via the electronic medical record after discharge:
 - Total morphine equivalents post-surgery, including and excluding recovery unit administration of narcotics in the immediate post-operative period.
 - Pain Visual Analog Score (VAS) score, which is obtained Q4 by nursing staff.
 - Timing and participation with physical therapy will be recorded looking at time until first therapy evaluation, and level of mobilization achieved
 - Length of stay, discharge disposition
- **Post-hospital follow-up:** Follow up after discharge will be done according to each individual surgeon's practice per their standard of care. It typically involves a follow up appointment at 2-4 weeks post-operatively, with longer follow-up as needed based on the injury type, surgical fixation strategy, and the trajectory of recovery. In addition to data collected as indicated above, including total morphine equivalents post-op period, CAM score, average pain VAS, length of stay, discharge disposition, timing/participation with inpatient physical therapy and adverse complications, data concerning 30-day patient readmission will be collected during the 30-day post-op period.

11. Data and Specimen Banking

No specimens will be obtained or retained for future study. The stored deidentified data from the study will be kept for a minimum of 6 years for records in the event follow-up studies are pursued and will remain protected and encrypted. Data will be permanently deleted following this time period. The banked data will be stored on a password-protected research drive corresponding to "orthotrauma (\\ummcnas03)". Upon conclusion of the study, the data will be stored in a password encrypted file that only the PI has access to.

12. Data Management

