No formal external recruitment methods will be used for this study, as hip fracture patients are universally admitted to the hospital after injury while awaiting surgery. Patients will be identified, screened, and approached for enrollment in the study as noted above (see 8. Study Timeline). After review and screening, the patient will be given the opportunity to ask researchers questions about the study. It will be reiterated to all patients during preoperative discussions that their enrollment status in no way will affect their ability to get adequate post-operative pain control. There will be no financial compensation in return for participation in this study.

25. Local Number of Subjects

The local recruitment goal at University of Massachusetts is 25 patients (Refer to 6. Study-Wide Number of Subjects)

26. Confidentiality

As part of our design, researchers will have access to patients' names and phone numbers in order to collect the required data. Upon enrollment, each patient will also be assigned a unique identifier. All patient personal information will be stored in a master list that links the patient's identifying information to their medical record number, which will be maintained in a separate, locked file that only approved research personnel will have access to. During the data collection period, researchers will not directly use this master list and, instead, will draw upon information from a separate that contains only the patient's first name, phone number, and unique patient identifier

All paper data collection documents are kept in locked file cabinets within locked offices that are accessible only to the project investigators and staff. All online databases are password protected to guard against unauthorized access and only approved research personnel will be granted access.

27. Provisions to Protect the Privacy Interests of Subjects (HIPAA)

All eligible subjects will be identified by orthopedic trauma team and researchers during morning intake rounds. After this point, only approved research personnel will have access to patients' private health information. All research will be stored electronically on secure research drives or locked offices as described above.

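### No pre-injection opioid, pain or CAM value is planned, so the opioid and VAS comparisons lose precision and delirium that began before the injection can dilute Aim 2

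*Protocol*

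**What the plan says.** **Outcomes.** Protocol Section 9 and the SAP give the same primary outcomes: "Total morphine equivalents in the post-operative period for 24, 48, and 72 hours, CAM score and average Pain Visual Analog Scale". None is a change score and none has a baseline.

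**Before surgery.** Section 24 says that "hip fracture patients are universally admitted to the hospital after injury while awaiting surgery". At enrolment (Section 10), "preoperative demographics will be recorded which will include age, sex, comorbidities, current use of anti-epileptic/anti-depressive medications for pain control, type of surgical approach", followed by ambulatory status and implant class. The one cognitive test before surgery is the Mini-COG: "A score of <4, which has been shown to have high sensitivity for dementia screening will define cognitive impairment and will preclude enrollment". Inability to consent, baseline dementia or cognitive deficit, and chronic opioid use are exclusions (Section 5). No limit is set on the time from enrolment to surgery.

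**After surgery.** The injection is given when the operation ends. The scheduled CAM is one "which will be administered 6 hours following surgery, post-operative day 1, 2 and 3 between 8AM-12PM". Further CAMs, once per nursing shift and when a provider is called for confusion, are listed under post-operative care. Two outcomes come from the electronic record: "Total morphine equivalents post-surgery, including and excluding recovery unit administration of narcotics in the immediate post-operative period", and "Pain Visual Analog Score (VAS) score, which is obtained Q4 by nursing staff". No start time is given for the VAS average.

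**Analysis.** Aim 2 states: "We hypothesize that total episodes of delirium will be decreased in the liposomal bupivacaine group". It also plans to compare average CAM scores. The SAP uses Student's t-test for continuous outcomes and chi-square or Fisher's exact test for categorical ones. It names no covariate and no rule separating new delirium from delirium already present.

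**The concern.** Treatment starts at the end of surgery, but the patient's course starts earlier. Section 4 treats pain after the injury as a common reason to operate, so patients can be expected to differ in pain and opioid need before they are treated. Where those differences carry over into the post-operative values, they add noise that a baseline measurement could remove. With about 25 patients per arm, that noise matters.

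Delirium raises a second issue. A patient can pass the Mini-COG, consent, become delirious while waiting for surgery, and still be CAM-positive 6 hours afterwards. That episode counts towards Aim 2 although it began before the drug was given. Such cases are expected equally in both arms, so they pull the comparison towards no effect. The Mini-COG and consent requirements act at enrolment only and cannot catch later onset. With no CAM between enrolment and injection, the data could not show afterwards which episodes were new.

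**Working it through.** **1. The plan's own figure.** Inputs from Protocol Section 6: 50 patients (25 per arm if 1:1), 0.52 mg/d taken as the SD, 80% power, alpha 0.05 (two-sided assumed). A two-sample t-test gives a detectable difference of 0.4205 mg/d, so the stated 0.42 reproduces. It is an unadjusted figure.

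**2. Precision for opioid use and VAS.** Let r be the correlation between the pre-operative value and the outcome. The documents give none, so r is an assumption. With one covariate and N = 50, the variance of the adjusted difference relative to the unadjusted one is

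(1 - r²) × (1 + 1/46),

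where 46 = N - 4 and the second factor is the price of estimating the slope. The equivalent unadjusted sample is 50 divided by this ratio. The detectable opioid difference is 0.4205 times its square root.

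| r | Variance ratio | Equivalent N | Detectable difference (mg/d) |
|---|---|---|---|
| 0.1 | 1.01 | 49.4 | 0.42 |
| 0.2 | 0.98 | 51.0 | 0.42 |
| 0.3 | 0.93 | 53.8 | 0.41 |
| 0.5 | 0.77 | 65.2 | 0.37 |
| 0.6 | 0.65 | 76.5 | 0.34 |

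Break-even is at r² = 1/47, so r is about 0.15. Below that, adjustment costs a little precision.

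**3. Dilution for delirium.** Let q be the proportion delirious before the injection and i the risk of new delirium in controls. Both are assumptions (3-10% and 10-20%), because the documents give neither. The drug is assumed to halve new cases and to leave existing ones unchanged. If every existing case is still positive at the first CAM,

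observed risk ratio = [q + 0.5·i·(1 - q)] / [q + i·(1 - q)].

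- q = 3%, i = 20%: 0.127 / 0.224 = 0.57. Share of control cases that predate the drug: 0.03 / 0.224 = 13%.
- q = 5%, i = 15%: 0.121 / 0.1925 = 0.63. Share: 26%.
- q = 10%, i = 10%: 0.145 / 0.19 = 0.76. Share: 53%.

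If half of the existing cases clear before the first CAM and do not recur, replace the stand-alone q by q/2 in both lines. The two ends become 0.112 / 0.209 = 0.54 and 0.095 / 0.14 = 0.68.

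**4. Power for delirium.** Same inputs, 25 per arm, normal approximation. Counting all cases, power is about 6-14%. Restricted to patients CAM-negative before the injection, with 25 × (1 - q) per arm, it is about 9-16%. The expected number of pre-injection cases is 25 × 0.03 = 0.75 to 25 × 0.10 = 2.5 per arm.

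**The case against.** The strongest reply is that randomization already deals with this. The arms are comparable in expectation and the planned t-test is valid, so adjusting for baseline is a choice about efficiency and corrects no error. That stands. The gain also depends on a correlation that the documents do not supply. Post-operative analgesia is standardized, chronic opioid users are excluded, and the pre-operative line of Appendix A shows no content. A weak correlation is therefore possible, and at r = 0.2 the gain is only one patient.

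A reader might infer that pre-operative pain and opioid use are themselves counted as results. The documents do not support that. Opioid totals are defined after surgery, and Aim 1 places pain assessment in the post-operative period. The VAS average lacks an explicit start time, which is a gap in definition and does not show that earlier scores enter. Nor does Section 24 say that patients are admitted in pain; it says that they are admitted and wait.

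On delirium, the range in step 3 has a demanding upper end. It pairs the highest assumed prevalence with the lowest incidence, in patients who had passed the cognitive screen, and it has every case persisting. The model is also a yes/no ratio, whereas the plan speaks of episodes and average scores. In a repeated measure, patients already delirious could still respond to treatment. These points limit the size of the effect. They do not remove the route by which earlier onset is counted.

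**Conclusion.** The omission is clear in both documents: no primary outcome has a pre-injection value, and none is analysed with adjustment. There is no average bias.

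For opioid use and VAS the loss is precision only. It is worth about 1 to 27 patients on a base of 50 if r is 0.2-0.6, and nothing below about 0.15. For delirium there is dilution of unknown size: an observed ratio of 0.57-0.76 in place of 0.50 under the stated assumptions with full persistence, and closer to 0.50 if some cases resolve.

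A reader might conclude that this omission is what would make a null delirium result uninterpretable. It is not. On these inputs power is below 20% with or without a pre-operative CAM, so sample size alone already prevents that reading. The case for the change is that it costs little, improves precision at plausible correlations, and lets new delirium be told apart from delirium already present.

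**What to change.** 1. **Opioid and VAS.** In the record extraction already planned, also take the mean VAS and the morphine equivalents per 24 hours from admission to operating-room entry. A rate is needed because waiting times will differ. Pre-specify the matching value as the covariate in an ANCOVA for each opioid and VAS outcome, and state that the VAS average starts at end of surgery.
2. **Delirium.** Add one pre-operative CAM, given by the staff who already administer the Mini-COG or the shift CAM, as close to surgery as practicable so that late onset is caught. Keep the all-randomized comparison as the main Aim 2 analysis, in line with the intention-to-treat commitment in Section 14. Add a pre-specified analysis of new delirium in patients CAM-negative before the injection. That subset is fixed before treatment and so cannot depend on it.

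The cost is slightly more chart extraction and one short CAM per patient, with no added patients or staff. Values already charted may be recoverable later, but a pre-operative CAM that was not done is not, so the second item must be settled before enrolment.
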